18.3.2. SECONDARY SAFETY ENDPOINT

There is one secondary safety endpoint in the study which is contrast sensitivity. Following Draft ANSI Z80-35 for Extended Depth of Focus Intraocular Lenses, monocular and binocular contrast sensitivity (photopic and mesopic with and without glare) in each eye and both eyes in the contrast sensitivity subgroup as measured by a computerized contrast sensitivity testing system at 6 months will be analyzed in the following manner (there is no specific hypothesis testing or success criterion):

- a. Between-eye mean difference in log contrast sensitivity (logCS) between IC-8 IOL eyes and their fellow control eyes with two-sided 90% confidence interval on the mean difference at each spatial frequency.
- b. Compare the mean binocular logCS between the test group and the control group with two-sided 90% confidence interval at each spatial frequency.
- c. Provide descriptive statistics for the logCS for each eye and both eyes (mean, standard deviation, two-sided 90% confidence interval, median, 0th, 25th, 50th, 75th, and 100th percentiles) and for each spatial frequency.
- d. Using a computerized contrast sensitivity testing system should minimize the floor and ceiling effects in contrast sensitivity testing. However, in the event that a subject is unable to see a targeted spatial frequency at the highest contrast possible in the display (e.g., 100% contrast), the highest contrast or, equivalently, the lowest contrast sensitivity score will be given, preceded by the appropriate inequality symbol (< or >) to indicate that the actual sensitivity is below the given value. The number and percentage of subjects who cannot see any contrast will be recorded and tabulated for each spatial frequency to provide a qualitative extent of the bias. Descriptive tables will include a note that the corresponding mean values are biased upward and variability values are biased downward (using < and > symbols).

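### Contrast sensitivity scores at the floor enter the planned mean differences and 90% intervals, and no floor-robust estimate is planned beside them

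*Combined protocol and SAP*

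**What the plan says.** Protocol section 18.3.2 makes contrast sensitivity the single secondary safety endpoint, measured at 6 months in a subgroup of at least 177 test and 59 control subjects (section 9.7).

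- Item a, monocular: "Between-eye mean difference in log contrast sensitivity (logCS) between IC-8 IOL eyes and their fellow control eyes with two-sided 90% confidence interval", at each spatial frequency.
- Item b, binocular: "Compare the mean binocular logCS between the test group and the control group with two-sided 90% confidence interval at each spatial frequency".
- Item c, descriptive summaries for each eye and both eyes, including "two-sided 90% confidence interval, median, 0th, 25th, 50th, 75th, and 100th percentiles".
- Item d, the floor rule. For a subject who cannot see the target at the display's maximum contrast, "the highest contrast or, equivalently, the lowest contrast sensitivity score will be given, preceded by the appropriate inequality symbol". The extent is to be shown by a count: "The number and percentage of subjects who cannot see any contrast will be recorded and tabulated for each spatial frequency". The caveat follows: "Descriptive tables will include a note that the corresponding mean values are biased upward and variability values are biased downward".

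On how often the floor will be reached, item d says only: "Using a computerized contrast sensitivity testing system should minimize the floor and ceiling effects in contrast sensitivity testing". On decisions, the section says: "there is no specific hypothesis testing or success criterion".

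**The concern.** A floor score is an upper bound on the eye's sensitivity: the true value lies below it. The plan flags it with an inequality symbol, but then averages it as if it were a measurement. The caveat is attached to means and variability in the descriptive tables. It does not mention the differences in items a and b, which are what a reader will use to judge whether the lens costs contrast.

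A difference is biased when the two sides are shifted by different amounts. If IC-8 eyes have a real loss and a spread similar to the fellow eyes, more of them sit at the floor, their mean is raised more, and the loss shrinks. Section 10.3 lists loss of contrast sensitivity among the potential risks, so a loss is plausible. Because the endpoint has no pass/fail rule, the estimate and its interval are the whole result.

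The planned floor count is per subject and per frequency. It is not explicitly split by eye or by arm, and that split is what would show the direction of any bias.

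**Working it through.** **Inputs in the documents.** The only figure is the subgroup size, 177:59, a ratio of exactly 3. No effect size, SD, alpha, power, correlation or floor rate is given, so the size cannot be reproduced. Solving a two-mean formula backwards with two-sided 0.05 and 80% power gives delta/SD = (1.960 + 0.842) × √((1 + 1/3)/59) = 0.421. Other combinations of alpha and power fit equally well.

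**Assumptions (not in the documents).** Normal logCS; SD 0.30 with between-eye correlation 0.5, or SD 0.35 with correlation 0.6; true loss 0.15 or 0.30; fellow-eye floor share 0.1% to 20%.

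**Formula.** Put the floor at 0, and let an eye's true mean be μ above it, with SD σ and a = μ/σ. After floor substitution the expected mean is μΦ(a) + σφ(a).

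**One case in full** (σ = 0.30, loss 0.15, 10% of fellow eyes at the floor):

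- Fellow eye: a = 1.282, μ = 0.384. Mean = 0.384 × 0.900 + 0.30 × 0.175 = 0.399.
- IC-8 eye: μ = 0.384 − 0.150 = 0.234, a = 0.782, floor share 21.7%. Mean = 0.234 × 0.783 + 0.30 × 0.294 = 0.272.
- Reported loss = 0.399 − 0.272 = 0.127 against a true 0.150, an understatement of 15%.
- SD of the paired difference without a floor: 0.30 × √(2 × 0.5) = 0.300, so the half-width is 1.645 × 0.300/√177 = 0.037. With the floor the SD is 0.266 (simulation) and the half-width 0.033.
- Bias/SE = −0.023/0.020 = −1.15. The nominal 90% interval therefore covers the true loss about 69% of the time.

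**Range, by the same steps, for 177 pairs:**

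| True loss, SD, correlation | Fellow / IC-8 at floor | Reported loss | Understated | Coverage of 90% interval |
|---|---|---|---|---|
| 0.15, 0.30, 0.5 | 0.1% / 0.5% | 0.150 | 0.2% | 90% |
| | 1% / 3.4% | 0.147 | 2% | 90% |
| | 5% / 12.6% | 0.137 | 8% | 84% |
| | 10% / 21.7% | 0.127 | 15% | 69% |
| | 20% / 36.6% | 0.108 | 28% | 25% |
| 0.30, 0.30, 0.5 | 0.1% / 1.8% | 0.298 | 0.6% | 90% |
| | 1% / 9.2% | 0.288 | 4% | 85% |
| | 5% / 26.0% | 0.259 | 14% | 36% |
| | 10% / 38.9% | 0.232 | 23% | 3% |
| | 20% / 56.3% | 0.189 | 37% | near 0% |
| 0.30, 0.35, 0.6 | 1% / 7.1% | 0.290 | 3% | 87% |
| | 5% / 21.5% | 0.264 | 12% | 50% |
| | 10% / 33.6% | 0.239 | 20% | 9% |

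**Cases that go the other way.**

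- With no true loss and equal SDs, both means shift equally and the bias in the difference is 0 at every floor share.
- With fellow eyes more variable (SD 0.40 against 0.25; means 0.50 and 0.45 above the floor; 10.6% against 3.6% at the floor), the reported loss is 0.520 − 0.454 = 0.067 against a true 0.05. That overstates the loss.

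**Item b.** The bias formula is the same, applied to binocular floor shares. With 177 against 59 subjects and SD 0.30, the half-width without a floor is 1.645 × 0.30 × √(1/177 + 1/59) = 0.074. The interval is wider than in item a, so a given bias costs less coverage.

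**Medians.** The difference between the two marginal medians stays at its true value while fewer than half the eyes on each side are at the floor. The median of the within-subject differences is not protected. In the case worked in full above, a simulation of one million pairs gives 0.115 against a true 0.150.

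**The case against.** The plan is open about the problem. It flags floor scores, counts them at each frequency, notes the bias in its tables, and reports medians and percentiles that resist a floor. It expects the computerized system to keep floor effects small. Appendix I has subjects tested with their best spherocylindrical correction, which also helps. If the floor is rarely reached, the bias is negligible, as the 0.1% rows show. No claim rests on a test of this endpoint. The analysis is said to follow a draft ANSI standard, and sections 18.0 and 18.4 defer further methods, including sensitivity analyses, to the SAP, whose own text is not in the document reviewed here. A censored model replaces an openly bounded value with an extrapolation that leans on the normal tail.

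Most of this stands, and it limits the point to a supplementary analysis. It does not remove it. The medians in item c are single summaries with no interval on their difference, and the note does not reach items a and b.

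A reader might go further and infer that the plan concedes it will understate any IC-8 contrast loss, or that the rule always favours the device. The documents support neither reading. The admitted bias concerns means and spread, not the difference. Its effect on the difference depends on floor shares that are not given, and it can be nil or reversed. Nor do the documents say at which frequencies or lighting conditions the floor will be reached.

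**Conclusion.** The point holds as a modest gap in the analysis plan. Items a and b include floor-substituted scores, and the protocol text gives no floor-robust version of either difference. When IC-8 eyes reach the floor more often with similar spread, the loss is understated by under 1% at a 0.1% fellow-eye floor share and by 28 to 37% at 20%, and the interval narrows. At n = 177 pairs, coverage suffers sooner than the percentages suggest: at a 5% fellow-eye floor share it is already 36 to 84%, depending on the assumed loss and SD. All these sizes rest on assumed normality, SDs, correlations and floor shares. No success decision changes; what is at stake is the accuracy of the estimate reported for the only secondary safety endpoint.

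**What to change.** Keep the planned means and 90% intervals. For items a and b, pre-specify beside them, at each spatial frequency and each lighting/glare condition where any eyes are at the floor, one of the following with a 90% interval:

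- a left-censored (Tobit-type) estimate, with a subject effect for the between-eye comparison; or
- the difference between the two marginal medians, with the interval obtained by resampling subjects. The median of within-subject differences should not be used.

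Tabulate the number and percentage at the floor separately for IC-8 and fellow eyes, and for test and control groups, with a 90% interval on each difference. Extend the table note to say that the mean difference and its interval are also affected, in a direction that depends on those percentages. If the SAP already provides this, a cross-reference in section 18.3.2 is enough.

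The cost is a little more analysis work, with no new data, subjects or visits. The censored model relies on approximate normality of logCS, most heavily where the floor share is high. The median difference stops being informative once half or more of the eyes on either side are at the floor.

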18.3.3. ADDITIONAL SAFETY ANALYSES

1. Monocular (measured in the IC-8 eyes in the test group the second eyes in the control group) and binocular low contrast (10%) uncorrected distance, intermediate and near visual acuities in the test group and control group at 6 months (to be performed in the contrast sensitivity subgroup with BCDVA 20/25 or better in each eye) will be analyzed in the following manner:

- a. Descriptive statistics (mean, standard deviation, two-sided 95% confidence interval) and vision level distributions (20/20, 20/25, 20/32, 20/40, 20/50, 20/63, 20/80 or worse) for both test and control groups.
- b. Comparison of mean UCDVA and mean BCDVA in the test group to mean BCDVA in the control group for monocular and separately for binocular visual acuities.
- c. Comparison of mean UCIVA and mean DCIVA in the test group to mean DCIVA in the control group for monocular and separately for binocular visual acuities.
- d. Comparison of mean UCNVA and mean DCNVA in the test group to mean DCNVA in the control group for monocular and separately for binocular visual acuities.
- 2. Descriptive statistics (mean, two-sided 90% confidence interval) for the rate of removals due to visual/optical reasons in the IC-8 eyes, fellow monofocal eyes, first eyes and second eyes in the monofocal control group.

18.4. DATA CONVENTIONS

Descriptive and summary statistics will typically include sample size (N), mean, standard deviation (SD), minimum (Min), and maximum (Max) as appropriate for continuous variables. For categorical data and some ordinal variables, the sample size, frequency and proportion will be computed. Each statistical comparison will be tested at two-sided $\alpha = 0.05$ unless otherwise specified. For continuous variables, statistical tests assuming normality will generally be used. However, the data will be reviewed to evaluate if the normality assumption is appropriate. If it is not, an appropriate transformation of the data (i.e., logarithmic) or the corresponding non-parametric tests may be used. Details for adverse event reporting, other data analysis not discussed in the protocol including stratification analysis and sensitivity analysis, sample size calculation and other statistical methods are specified in the SAP.

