18.0 DATA ANALYSIS METHODS

This section (section 18.0 through 18.4) highlights the key statistical methods and analyses planned for this study. The SAP includes details for all statistical methods, plans, adverse events reporting methods, and sample size calculations for the study.

Some key data and analysis conventions include the following:

For the primary and secondary effectiveness endpoints, the six-month postoperative visit will be the primary analysis time point unless otherwise noted. For the primary safety endpoints, the 12-month study visit will be the primary analysis time point.

Binocular safety and effectiveness analyses will compare the test group and the control group. Monocular safety and effectiveness analyses will compare the IC-8 IOL eyes and the monofocal fellow eyes within the test group. All co-primary effectiveness and safety endpoints have to be met to claim overall effectiveness and safety success. There is one secondary effectiveness endpoint regarding the tolerance to astigmatism in IC-8 IOL eyes, and this endpoint will only be tested when all co-primary effectiveness endpoints have been achieved. Under this plan, type I error rates will be controlled at a significance level of 0.05 per individual hypothesis without adjustment for multiplicity under any family. Other statistical comparisons in the additional analyses and supportive analyses should not be used for the purpose of claims.

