18.1. ANALYSIS POPULATION

For the primary effectiveness endpoints, the primary analysis population will be an ITT (Intentto-Treat) analysis. The ITT population includes all subjects who are fully enrolled and are binocularly implanted in the study. For the secondary effectiveness endpoint, the primary analysis population will be a mITT (modified Intent-to-Treat) analysis for all eyes implanted with IC-8 IOL and achieving BCDVA 20/25 or better. For eyes that do not have data available at the 3-, 6- or 12-month visits, data will be imputed according to the imputation methods specified in the SAP.

A Per-Protocol (PP) analysis will also be performed on the primary and secondary effectiveness endpoints to support the primary ITT analysis. The PP population will include eyes from binocularly implanted subjects, evaluated within the proper study interval and without major protocol deviations as determined prior to database lock, and evaluated at least two weeks after any SSIs. Major protocol deviations to be excluded from PP analysis are: those related to inclusion, exclusion or qualification criteria, and/or those that have the potential to either positively or negatively affect the primary and secondary study endpoints, including uncorrected or distance-corrected visual acuities, refraction, contrast sensitivity, and are unrelated to the study procedure or the study device; and they will be specified prior to database lock.

PP analyses will only include available data at the time of analysis (i.e., no data imputation). For the primary effectiveness endpoints, the PP population is usually a subset of the ITT population; for the secondary effectiveness endpoint, the PP population is usually a subset of the mITT population.

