18.2. EFFECTIVENESS ANALYSES

All co-primary effectiveness endpoints need to be achieved to claim overall effectiveness success. Therefore no multiplicity adjustment is necessary for primary effectiveness endpoints. The secondary effectiveness endpoint will be tested after the primary effectiveness endpoints have been achieved. The secondary effectiveness endpoint needs to be achieved to support the astigmatism tolerance claim. For the primary effectiveness endpoints, the primary analysis population will be the ITT analysis population. For the secondary effectiveness endpoint, the primary analysis population will be a mITT analysis population. The PP analysis population will also be used on the key effectiveness endpoints to support the primary ITT analyses.

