18.2.2. SECONDARY EFFECTIVENESS ENDPOINT

There is one secondary effectiveness endpoint in the study, which is assessing tolerance to astigmatism in IC-8 IOL eyes at 3 months (analysis done on IC-8 IOL eyes with

BCDVA 20/25 or better) by comparing eyes with 1.0 to 1.5 D of preoperative corneal astigmatism (Astigmatism Group 2) to eyes with < 1.0 D of preoperative corneal astigmatism (Astigmatism Group 1):

a. The mean UCDVA from Astigmatism Group 2 is non-inferior to that from Astigmatism Group 1 using a margin of 0.12 logMAR (equivalent to 6 letters on ETDRS chart). The comparison between Astigmatism Group 2 and Astigmatism Group 1 for the mean monocular UCDVA (logMAR) will be performed using a ttest for non-inferiority at $\alpha = 0.05$ (one-sided). The null hypothesis is that the mean acuity in Astigmatism Group 2 is inferior to Astigmatism Group 1 by 0.12 logMAR or more. The alternative hypothesis is that the mean acuity in Astigmatism Group 2 is inferior to Astigmatism Group 1 by less than 0.12 logMAR. Formally put as follows:

$$\begin{split} H_0 &: \mu_T - \mu_C \geq 0.12 \\ H_A &: \mu_T - \mu_C < 0.12 \end{split}$$

Where μ_T is the mean logMAR acuity from Astigmatism Group 2 and μ_C is the mean acuity from Astigmatism Group 1.

The statistical success criterion is when H_0 is rejected by a p-value less than 0.05, demonstrating the mean monocular UCDVA from Astigmatism Group 2 is statistically non-inferior to the mean monocular UCDVA from Astigmatism Group 1 using a margin of 0.12 logMAR.

- b. Scatter plot and regression analysis will be generated to depict the mean uncorrected visual acuities (separately for UCDVA, UCIVA and UCNVA) as a function of preoperative corneal astigmatism.
- c. No claim will be made with regard to comparing IC-8 IOL to the monofocal or monofocal toric IOL.

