18.2.4. ADDITIONAL EFFECTIVENESS ANALYSES

1. Compare mean monocular uncorrected distance (UCDVA), intermediate (UCIVA) and near (UCNVA) visual acuity of the IC-8 eyes to the fellow control eyes.

- 2. Binocular +0.75 D Distance Corrected Visual Acuity compared between the test group and the control group: +0.75 D distance correction will be achieved by correcting all eyes in both groups with their best distance-corrected refraction and then placing a +0.75 D lens in front of the IC-8 IOL eyes in the test group and in front of the second eyes in the monofocal control group.
 - Binocular +0.75 D Distance Corrected Intermediate Visual Acuity (+0.75 DCIVA): Proportion of subjects achieving 20/25 or better in the test group is at least 25% more than the control group.
 - Binocular +0.75 D Distance Corrected Near Visual Acuity (+0.75 DCNVA): Proportion of subjects achieving 20/40 or better in the test group is at least 25% more than the control group.
 - c. Binocular +0.75 D Distance Corrected Distance Visual Acuity (+0.75 DCDVA): Proportion of subjects achieving 20/25 or better in the test group is not less than the control group by more than 10%.
 - d. The monocular visual acuities from the IC-8 IOL eyes in the test group will be similarly compared to the second eyes in the control group.
- 3. Supportive analyses:
 - a. The monocular co-primary endpoint analyses on DCIVA and depth of focus will be repeated by comparing IC-8 IOL eyes to the second eyes in the control group to support the primary endpoint analyses.
 - b. The co-primary endpoint analyses on binocular UCDVA, UCIVA, UCNVA and monocular DCIVA will be repeated at 12 months to support the primary endpoint analyses performed at 6 months.
 - c. The secondary endpoint on tolerance to astigmatism in IC-8 IOL eyes is repeated on the postoperative refractive cylinder with the same grouping and test to support the results from preoperative corneal astigmatism and to check the influence from postoperative refractive cylinder on the effectiveness of the device.

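### Section 18.4 lets a log transform or rank test replace the t-tests on mean logMAR and does not exempt the co-primary and secondary tests

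*Combined protocol and SAP*

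**What the plan says.** Protocol section 18.4 (Data conventions) covers continuous variables as a class. Normal-theory tests are the usual choice, but "the data will be reviewed to evaluate if the normality assumption is appropriate", and if it is not, "an appropriate transformation of the data (i.e., logarithmic) or the corresponding non-parametric tests may be used". The section gives no criterion, timing or masking for that review and no rule for choosing between the two alternatives. It excludes no endpoint. Its proviso about other specification attaches only to the two-sided 0.05 level.

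The key comparisons are specified elsewhere as t-tests on mean logMAR:
- 18.2.1 items 1a, 2a and 4a: superiority for binocular UCIVA, binocular UCNVA and monocular DCIVA.
- 18.2.1 item 3a: non-inferiority for binocular UCDVA, margin 0.1.
- 18.2.2 item a: the astigmatism comparison "for the mean monocular UCDVA (logMAR) will be performed using a ttest for non-inferiority", margin 0.12.
- 18.3.1 item 1a: non-inferiority for BCDVA, margin 0.1.

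Item 4a and the synopsis call the IC-8 versus fellow-eye DCIVA comparison a two-sample t-test. Item 1a of 18.3.1 does not say whether its t-test is paired.

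Section 18.0 states that "type I error rates will be controlled at a significance level of 0.05 per individual hypothesis". Section 18.2 adds: "The secondary effectiveness endpoint needs to be achieved to support the astigmatism tolerance claim". On methods, 18.0 refers onward: "The SAP includes details for all statistical methods". Section 18.4 does the same.

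**The concern.** The hypotheses and margins are differences in mean logMAR. If normality is judged unsuitable, 18.4 would allow the deciding test to be one that addresses a different quantity. The error rate of that test for the stated hypothesis need not then be the 0.05 that 18.0 promises, and it can move in either direction.

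The secondary endpoint is the most exposed, because a single t-test decides the astigmatism claim. The other looks at that question do not decide it. On the per-protocol set, 18.1 says: "A Per-Protocol (PP) analysis will also be performed on the primary and secondary effectiveness endpoints to support the primary ITT analysis". On the cylinder analysis, 18.2.4 says: "The secondary endpoint on tolerance to astigmatism in IC-8 IOL eyes is repeated on the postoperative refractive cylinder", and lists it as supportive. The regression in 18.2.2 item b carries no success criterion.

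No opportunistic choice is needed for this to arise. It follows from using the clause as written.

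**Working it through.** The plan has no figure of its own to reproduce here: the supplied text gives no SD, distribution shape or power for these tests. The group sizes are the Table 3 completers: 300 test and 100 control, with the test arm split 250 (below 1.0 D) and 50 (1.0 to 1.5 D). The actual numbers in the 3-month mITT set may differ. All SDs, shapes and SD ratios below are assumptions.

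**Log transform.** logMAR is 0 at 20/20 and negative when acuity is better. For a normal distribution the share with no logarithm is P(logMAR ≤ 0) = Φ(−mean/SD). With SD 0.10:
- mean 0.00: Φ(0) = 50%
- mean 0.05: Φ(−0.5) = 31%
- mean 0.10: Φ(−1) = 16%

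Adding a constant removes the gap but not the margin problem. With log(logMAR + 0.3), a 0.12 difference becomes:
- from reference 0: ln(0.42/0.30) = 0.336
- from reference 0.1: ln(0.52/0.40) = 0.262
- from reference 0.2: ln(0.62/0.50) = 0.215

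One logMAR margin therefore corresponds to no single margin on the new scale.

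**Rank test, secondary endpoint.** Subtract the margin from the Group 2 values and apply a Mann-Whitney test. This asks whether P(X − 0.12 < Y) differs from one half, which agrees with a mean difference of 0.12 when the two distributions share shape and spread. Simulation: 50 versus 250 eyes, true mean difference equal to the margin, one-sided 0.05, complete data, standardised gamma (normal for skewness 0), 40,000 trials per cell. Rejection rates in %:

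| SD ratio (50-eye / 250-eye) | 0.67 | 0.8 | 1 | 1.25 | 1.5 |
|---|---|---|---|---|---|
| Normal: rank | 2.9 | 3.5 | 5.1 | 6.3 | 7.6 |
| Normal: Welch | 5.2 | 4.9 | 5.1 | 4.9 | 5.2 |
| Normal: pooled | 1.6 | 2.8 | 5.2 | 7.7 | 10.4 |
| Skewness 1: rank | 0.3 | 1.3 | 5.0 | 12.3 | 19.4 |
| Skewness 1: Welch | 5.6 | 6.2 | 6.2 | 6.4 | 6.3 |
| Skewness 1: pooled | 1.3 | 2.6 | 4.7 | 7.8 | 10.7 |

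At skewness 2 and equal SDs, Welch gives 7.2% and pooled 4.2%.

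A second model used whole-letter data (0.02 logMAR) with a poor-acuity tail of +0.4 logMAR in Group 2 only (20,000 trials). With a 5% tail the rank test gave 12.6% and Welch 6.3%; with an 8% tail, 17.7% and 6.5%.

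**Would a criterion be enough?** Take one possible rule: Shapiro-Wilk at 0.05 on group-centred residuals, rank test if rejected, otherwise Welch (10,000 trials). Over the five SD ratios it switched in 86–88% of trials at skewness 0.5, with an overall error of 1.8–11.5%. At skewness 1 it switched in every trial (0.4–19.8%). A stated trigger of this kind fixes when the switch occurs, not what the replacement tests.

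**Binocular UCDVA, 300 versus 100, margin 0.1, skewness 1.** Rank test at control/test SD 0.67, 0.8, 1, 1.25, 1.5: 19.3%, 11.5%, 4.7%, 2.3%, 1.3%. Criterion 3b also requires at least half of test subjects at 0.1 or better. At a true deficit of 0.1 with SD 0.10, that expected share is Φ((0.1 − (control mean + 0.1))/0.10), which is 69%, 50% or 31% for control means of −0.05, 0 and 0.05.

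**BCDVA, 300 pairs, if analysed as paired (20,000 trials).** Signed-rank gives 9.7%, 17.2% and 40.6% at skewness 0.25, 0.5 and 1 of the within-subject differences, and 2.4%, 1.1% and 0.1% at the same negative values. The paired t-test stays at 4.4–5.5%.

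**Paired eyes.** For n subjects, Var(mean difference) = (σ₁² + σ₂² − 2ρσ₁σ₂)/n; a two-sample test omits the last term. With equal SDs the true standard error is √(1 − ρ) times the two-sample one, for example √0.5 = 0.71 at an assumed ρ of 0.5. Positive correlation makes the two-sample test conservative.

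**The case against.** The strongest reply is that the specific sections govern. They commit each comparison to a t-test, define success by its p-value and state hypotheses in means, while 18.4 is a general convention in permissive language. That reading is fair, but 18.4 does not state it. The SAP may also settle the matter. Its text was not supplied, so a reader who infers that the trial has no rule at all goes further than the documents allow.

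It is also tempting to say that neither alternative can ever test the stated hypotheses. For the rank test that is too strong: at equal SDs and common shape it holds about 5%. Its large rates need skewness together with an SD imbalance in one direction, and the opposite imbalance makes it conservative. With normal data and unequal SDs it is closer to 5% than a pooled t-test. On the log, 18.4 asks for an appropriate transformation, and one undefined at 20/20 arguably is not; but the log is the only example the clause names.

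A reader might take 19% as a false-claim rate. It is a single-test rate under assumed inputs. Co-primaries need every criterion met, and the secondary is tested only after all the effectiveness co-primaries succeed. No stand-alone rank-test rate is available for items 1a, 2a or 4a. In a simulation of UCIVA at equal means (assumed means 0.05–0.2, test SD 0.12, SD ratio 0.67–1.5, skewness 0 or 1), the rank test and criterion 1b passed together in at most 0.05% of trials. Entry rules on first-eye acuity, and the 20/25 BCDVA restriction for the secondary, may also limit tails; the simulations do not model them.

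**Conclusion.** The point stands as a gap in the protocol text: 18.4 permits a switch to tests that do not, in general, carry the stated mean hypotheses and margins, and it exempts none of the six t-tests. The log part follows from the logMAR scale itself. The rank part depends on shapes and SDs that the documents do not give. For the secondary endpoint the assumed range is about 0.3% to 19%, with about 5% at equal SDs. The consequence for co-primary claims is smaller.

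A reader might also infer that exempting the tests is a complete cure. It is not: a locked pooled t-test still reaches about 10% at 50 versus 250 with an SD ratio of 1.5, and Welch keeps a small excess (about 6–7%) under skewness. The t-test version therefore has to be fixed as well. This change should be made; confidence is moderate, mainly because the SAP text was not supplied.

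**What to change.** - In 18.4, state that the normality review and the switch do not apply to 18.2.1 items 1a–4a, 18.2.2 item a or 18.3.1 item 1a. These stay as t-tests on untransformed logMAR, with rank analyses as sensitivity only.
- Remove the logarithmic option for logMAR.
- State in advance whether the between-group t-tests are pooled or Welch. Welch is the safer choice if SDs may differ, at the price of the small excess shown above.
- In the synopsis and 18.2.1 item 4, replace the two-sample test for IC-8 versus fellow-eye DCIVA with a paired t-test, and name a paired t-test for BCDVA in 18.3.1 item 1a.
- If the SAP already fixes these tests, align the protocol wording and cross-refer from 18.4.

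Cost: a few sentences in the protocol and matching SAP text, with no new data and no change in sample size.
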